7.2 Statistical Methods

Data will be analyzed by a statistician blinded to drug assignment. Demographic comparisons to assess effectiveness of randomization will be examined between treatment arms by ANOVA and chi-square tests where appropriate. Differences in baseline values for all variables between treatment arms will be assessed using ANOVA. The paired differences in these same variables will be compared after the 6-week study period. These values include all measured physiologic variables, such as resting heart rate, blood pressure, plasma catecholamine concentrations, MSNA, cerebral blood flow, forearm blood flow, flow-mediated vasodilation, pulse wave velocity, augmentation index, polysomnographic measures, Pcrit, apnea threshold, and others.

The primary outcome variable is the difference in the individual slope of the MSNA – SaO₂ response curve at 6 weeks and baseline between treatment groups. The MSNA – SaO₂ response curve will be graphed with MSNA as the dependent variable and SaO₂ as the independent variable during progressive hypoxia. Slope response curves will also be calculated for heart rate, ventilation, forearm blood flow, cerebral blood flow, and blood pressure during hypoxia, hyperoxia and controlled breathing periods. MSNA will be expressed as burst frequency (bursts/min), burst amplitude (arbitrary units) and total minute activity (burst frequency x mean burst amplitude). MSNA will be averaged over the 5-min measurement periods at baseline, 90%, 85%, 80% hypoxia, and during controlled breathing. During hyperoxic trials, 15-sec averages of MSNA will be obtained, and an average of the 4 trials will be computed. The slope response of MSNA during progressive hypoxia will be calculated and will be analyzed using ANOVA. Changes in polysomnographic measures from baseline to the end of the 6-week treatment period between the treatment groups will be compared using ANOVA. If significant ANOVA p-values are found, then post-hoc multiple comparison Tukey HSD tests will examine differences between each arms. Multiple regression will be used to determine the influence of subject characteristics and hours of CPAP use on the primary outcome, and on the effect of treatment on the primary outcome.

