Any deviations from the protocol at any of the research sites will be discouraged and if occur, will be reported to the UW HS IRB if the deviation or exception presents a significant safety risk to the subject or potential subject. As per Good Clinical Practices, protocol deviations will be documented and reviewed at the quarterly investigator meetings. If changes are necessary for the project, protocol modifications will be submitted to the HS IRB to change the protocol to fit the required changes.

6.5 *Unexpected Findings*

Whenever tests like the electrocardiogram (Visit 1), cardiac output (Visits 3 and 6), or serum laboratory tests are done, there is the chance of an unexpected finding. Subjects will be informed of all findings of clear clinical significance which may be revealed during the electrocardiogram, cardiac output procedure (limited echocardiography), and serum laboratory tests. Findings of clear clinical significance are those for which we generally know the risks of non-treatment and for which treatment may be available. If unexpected findings for the electrocardiogram, cardiac output, or serum laboratory tests are discovered, a letter describing the findings will be sent to the subject and to his/her physician with permission from the subject.

7 Statistical Plan

7.1 *Sample Size Determination*

The primary outcome will be the change in the slope response of MSNA during progressive hypoxia from baseline to 6 weeks. From previous data from our lab we have seen an approximate standard deviation for slope in OSA patients under similar progressive hypoxia of 8-10.

Based on interim data, a power calculation for the differences and standard deviations in primary outcome variable estimated that we would have 90% power (this is increased power from our original sample size calculation that used 80%) to determine a difference of 3.07 (1.13 vs -1.94) at a significance level of 0.017 (Bonferroni adjusted alpha for 3 tests) if we had complete MSNA slope response data from 20 subjects per group.

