We had originally proposed to enroll 50 subjects per group. Our interim analysis determined that if we obtain complete data in 20 subjects per group, we are likely to find a significant difference. We will enroll as many subjects as we can in the remaining time frame to give us the best possible chance at finding a difference. Consistent with DMC recommendations, we will reduce our sample size to 100 subjects. To account for drop-outs, we will ask to enroll 120 subjects to get 100 subjects who proceed to randomization.

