8.5 Stopping Rules

In case there is a significant beneficial or harmful effect due to one or both of the treatment arms, which would require early termination of the study, we plan on having three interim data analyses. Interim analysis will be performed after approximately 33%, 66%, and 100% of the subjects complete the 6-week study period. Stopping criteria for benefit/harm will be based on the primary outcome variable analysis with O'Brien-Fleming alpha spending thresholds for three interim analyses. These thresholds are: $p=0.0005$ at look 1, $p=0.01413$ at look 2, and $p=0.04507$ at final analysis. The DMC, concurrent with and additional to the interim analyses, will meet on a quarterly basis to evaluate the protocol, subject accrual rates, subject retention, adverse events, and other aspects of the study. In those meetings which correspond to the times determined for interim analyses the DMC will also evaluate the benefit or harm of the treatments.

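### The primary ANOVA on change in MSNA slope is valid but omits baseline slope and the CPAP randomisation stratum, so it may lose some precision (minor)

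*Combined protocol and SAP*

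**What the plan says.** Sections 3.2, 7.1 and 7.2 define the primary outcome as the change in each subject's MSNA–SaO₂ slope between baseline and 6 weeks, compared across three arms. Section 7.2 gives the test: "The slope response of MSNA during progressive hypoxia will be calculated and will be analyzed using ANOVA". If the ANOVA is significant, "post-hoc multiple comparison Tukey HSD tests will examine differences between each arms". Baseline slope enters only by subtraction.

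Sections 3.1 and 5.3 stratify randomisation by average nightly CPAP use in three categories (under 1 hour, 1 to 4 hours, over 4 hours), in permuted blocks. The primary ANOVA names no stratum term.

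Section 7.2 also plans a multiple regression on the "influence of subject characteristics and hours of CPAP use on the primary outcome, and on the effect of treatment on the primary outcome". It is not described as the primary test. It names neither baseline slope nor the stratum, and it does not say whether CPAP hours are those before or during treatment.

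Section 7.1 claims 90% power with 20 complete subjects per group "to determine a difference of 3.07 (1.13 vs -1.94) at a significance level of 0.017 (Bonferroni adjusted alpha for 3 tests". It also cites an "approximate standard deviation for slope in OSA patients under similar progressive hypoxia of 8-10". It gives neither the SD of the change nor the correlation between visits.

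**The concern.** A change score fixes the coefficient of the baseline value at 1. With equal variances at the two visits the best coefficient is r, so subtracting the whole baseline adds noise whenever r is well below 1. A stratum that predicts the outcome but is left out of the model also leaves its variance in the error term.

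Baseline slope (Visit 3) and the stratum are already collected for subjects with a usable primary outcome. Section 7.1 treats 20 complete subjects per group as enough: "Our interim analysis determined that if we obtain complete data in 20 subjects per group, we are likely to find a significant difference". If that is all the trial obtains, precision lost in the model would matter more than in a larger trial.

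**Working it through.** **Inputs.** From section 7.1: difference 3.07, alpha 0.017, power 90%, 20 complete per group, slope SD 8–10, 100 randomised. From sections 3.1 and 5.3: three strata. Assumed: two-sided test, equal allocation, equal slope variance at both visits.

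**1. The plan's own figure.** The SD of change is not stated, so 90% power cannot be reproduced forwards. Solving backwards:

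SD = 3.07 × √(20/2) / (2.387 + 1.282) = 9.708 / 3.669 = 2.65 (normal approximation).

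With the noncentral t it is 2.55 (38 df) or 2.58 (57 df, the three-arm error term). I use 2.58.

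**2. Implied correlation.** For equal variances, SD²(change) = 2 × SD²(slope) × (1 − r), so r = 1 − 2.58² / (2 × SD²).

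- Slope SD 8: r = 1 − 6.656/128 = 0.948.
- Slope SD 10: r = 1 − 6.656/200 = 0.967.

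This holds only if 8–10 and 3.07 are on one scale. Sections 3.2 and 7.2 list three MSNA scales (burst frequency, burst amplitude, total minute activity) and do not say which the primary slope uses.

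**3. Effect of adjusting.** In large samples the variance of ANCOVA relative to change-score ANOVA is (1 + r)/2. In small samples this is multiplied by about 1 + q/(N − k − q − 1), with q covariate degrees of freedom and k arms. For baseline alone with 60 subjects the factor is 1 + 1/55 = 1.018.

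The full model was simulated at 20 per arm. Further assumptions, none in the documents: 99 randomised in stratified blocks of six, strata shares 40/20/40%, completion at random, a non-prognostic stratum. The slope SD column is 2.58/√(2(1 − r)).

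| r | Variance ratio | Power, ANCOVA vs ANOVA | Slope SD needed |
|---|---|---|---|
| 0.5 | 0.76 | 96.5% vs 90.2% | 2.6 |
| 0.7 | 0.88 | 93.4% vs 89.8% | 3.3 |
| 0.8 | 0.94 | 92.0% vs 89.9% | 4.1 |
| 0.9 | 0.98 | 89.6% vs 89.3% | 5.8 |
| 0.948 | 1.01 | 89.5% vs 89.8% | 8 |
| 0.967 | 1.02 | 89.0% vs 89.6% | 10 |

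A repeat gave 0.78, 0.87, 0.92, 0.99 and 1.00–1.01 over the same range, so the second decimal should not be pressed. If the stratum explains 10% of residual variance (assumed), the ratio at r = 0.948–0.967 is about 0.95–0.98. Both estimators centred on the true difference (3.06–3.08).

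Under Tukey HSD (per-pair alpha 0.0194) the pattern is the same: 90.9% unadjusted, against 97.1% at r = 0.5 and 94.9% at r = 0.7.

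**4. Break-even.** Setting the product in step 3 to 1 gives r = 2/factor − 1.

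- 60 subjects, baseline only: 2/1.018 − 1 = 0.96.
- 60 subjects, three covariate df: factor 1 + 3/53 = 1.057, r = 0.89. Stratified allocation makes the stratum terms cheaper; the simulation puts this near 0.93.
- 100 subjects: 0.98 (one df) and 0.94 (three df).

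Break-even is therefore a range of roughly 0.9 to 0.98, not a threshold.

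**5. More evaluable subjects.** With SD 2.58, unadjusted power is 95.9% at 25 per arm, 98.4% at 30 and 99.1% at 33. What remains below 100% is 4.1, 1.6 and 0.9 points.

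**The case against.** The strongest reply is that the plan's only printed figures point to no gain. Taken on one scale they put r at 0.95–0.97, where adjustment is neutral or costs 1–2% of variance. This stands, subject to the open question of scale.

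A reader might infer from the table that the plan gives up several points of power. The documents do not support that. A gain of that size needs r of about 0.7 or less, hence a slope SD of about 3.3 or less where section 7.1 cites 8–10. It also needs only 20 evaluable subjects per arm, whereas the plan is to randomise 100 and says "We will enroll as many subjects as we can in the remaining time frame". A reader might also take 0.93 as the correlation above which adjustment does not pay. That figure rests on strata shares, block size and a completion pattern that the documents do not give. Nor does the omission make the test biased or invalid: leaving out a balanced stratum makes the standard error, if anything, too large.

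The planned regression on CPAP hours partly covers the stratum, since the strata are cut from nightly hours. It does not settle the point, because it is not the primary test and does not name baseline slope.

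Finally, changing the primary model after an interim look can do more harm than a small loss of precision. This is right and shapes the fix.

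Against all this, r of 0.95 or more should not be presumed. Each slope rests on a few averaged oxygen levels, and section 7.3 accepts slopes from incomplete hypoxia runs.

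**Conclusion.** The point holds as a minor one. The primary ANOVA is valid and unbiased over randomisations, but it leaves out baseline slope and the randomisation stratum, and so may lose precision.

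How much is unknown, because r is not given. If the slope SD and the 3.07 difference share a scale, adjustment is roughly neutral: variance ratio about 1.00–1.02, or about 0.95–0.98 if the stratum explains 10% of residual variance. If the scales differ and r is 0.5–0.8, variance falls by about 6–24% at 20 evaluable per arm, but the power gain is only 1–4 points at best at 25–33 per arm.

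These sizes rest on a two-sided test, equal variances at both visits, a change SD of 2.58 inferred from the stated power, and the simulation settings listed above.

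**What to change.** By a dated amendment before unblinding and the final analysis, pre-specify an ANCOVA of 6-week slope on treatment, baseline slope and the three-level CPAP stratum, with multiplicity-adjusted pairwise comparisons from that model. State the MSNA scale, the SD of change and, if it can be had from pooled data without arm labels, r.

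Make the ANCOVA primary only if the choice can be documented as blind to arm-level data. Interim results have already been used to resize the trial, and section 7.1 prints two interim values (1.13 and −1.94). If that blindness can be documented, keep the change-score ANOVA as supporting. If it cannot, keep the change-score ANOVA primary and pre-specify the ANCOVA as supporting. In either case say which model governs any threshold still to be applied under section 8.5, where "Stopping criteria for benefit/harm will be based on the primary outcome variable analysis".

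The cost is no new data and about three degrees of freedom (57 to 54 at 20 per arm). Variance may rise by up to 1–2% if r is very high and the stratum is not prognostic. If the ANCOVA becomes primary, there is also a documented change of model after an interim look.

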7.3 Subject Population(s) for Analysis

This study will follow a Intent to Treat (ITT) philosophy. Loss to follow-up is a possibility and can cause issues with final analysis because the “missingness” of the data may not be random. We will try to determine if there is any cause for drop out and summarize the reasons accordingly. We have accounted for drop outs in our projected sample sizes to assure sufficient power to remain in our tests. We will test the sensitivity of the analysis results by comparing the analysis between dropping those with missing data and utilizing last observation carried forward. In regard to the measurements taken at each time period, if a subject is unwilling or unable to complete the full progressive hypoxia we will calculate the slope for that individual based on the data we were able to attain and use that in the final analysis.

8 Safety and Adverse Events

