Subjects will have 24-hour ambulatory blood pressure and 24-hour Holter/Heart rate variability measurements taken* (Visit 2) on a day/night prior to Visit 3. Prior to starting study drug therapy, subjects will come to the Clinical Research Unit (CRU) at the University of Wisconsin for physiology/vascular study (Visit 3). Subjects recruited from the other recruitment sites will come to Madison for Visit 3. Subjects will arrive on day one of their study, and will have physiologic assessments taken before full overnight polysomnography and overnight Holter/Heart rate variability* is completed during night one (to determine severity of OSA). Prior to polysomnography, subjects will have muscle sympathetic nerve activity, forearm blood flow, cerebral blood flow velocity, plasma catecholamines, ventilation, blood pressure, and heart rate measured at rest under normoxic (room air) conditions and during graded levels of hypoxia (90%, 85% and 80% SaO₂). Following this, subjects will be allowed to return to normoxia (room air levels of oxygen ~ 21% oxygen) and after dinner will be hooked up for polysomnography and Holter/Heart rate variability*. The morning after polysomnography, subjects will have assessment of brachial artery flow-mediated vasodilation and nitroglycerin induced vasodilation measured by ultrasound. Then subjects will have aortic pulse wave velocity and augmentation index measured by arterial tonometry. The 2nd night subjects will stay overnight again in the VA Research Unit and have control of breathing studies completed (Pcrit and apnea threshold). Subjects will initiate study drug treatment and will return two weeks later for a blood pressure and heart rate (office blood pressure) measurement, CPAP assessment, and safety assessment to measure serum creatinine and serum potassium concentrations. This is standard safety monitoring in patients taking ARBs, and to maintain blinding, all subjects will have this monitoring completed. Subjects who do have clinically significant increases in serum creatinine (an increase > 0.5 mg/dL) or whose serum potassium increases to a concentration > 5.0 mEq/L will have their participation in the study terminated. Subjects continuing in the study will then complete four additional weeks of drug therapy. At the end of six weeks of study medication, subjects will have 24-hour ambulatory blood pressure and 24-hour Holter/Heart rate variability assessed one day and night.

Version: 23, 7-25-17

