4.4 Early Withdrawal of Subjects

4.4.1 When and How to Withdraw Subjects

Allopurinol

If a subject experiences an adverse effect that is thought to be significant or serious (e.g. renal impairment, maculopapular rash, etc.) subjects' participation in the study will be ended.

Losartan

If a subject experiences clinically significant/serious adverse effects (angioedema, myalgias, acute renal failure), their participation will be ended. If the subject experiences increases in serum creatinine (> 0.5 mg/dL) or serum potassium (above 5.0 mEq/L) the subject's participation in the study will be ended. Blood pressure will also be measured at the two week monitoring visit (Visit 4). The dose of losartan will increase to 100mg daily if systolic blood pressure is > 120 mm Hg. For a systolic blood pressure between 100-120 mm Hg the subject may have dose increased if approved by study physician. If the subject's blood pressure is $< 100/60$ mm Hg and if the patient is dizzy and symptomatic during the study, the subject will discontinue study medication and go off study. This can be done via a phone encounter or via an additional (unexpected) visit. It is possible the subject's participation will be terminated if the study physicians feel that is appropriate.

Subjects may also be withdrawn from the study if they are diagnosed with a new and significant medical problem (e.g. they are hospitalized for an acute illness or major medical condition). Subjects may also be withdrawn from the study if they consistently fail to adhere to the protocol requirements. Study physicians will communicate with subjects' regular physician about care plans upon their withdrawal from the study.

Version: 23, 7-25-17

Additional (Unexpected) Visit:

If a subject experiences an adverse event that requires them to be seen by study staff, they should be scheduled for a visit to their local center as soon as is feasible. The PIs should be notified immediately and the physician at the local site should see the subject during the visit. Depending on the complaint, the AE should be evaluated with appropriate objective measures (blood tests, blood pressure/heart rate measurements, etc.) and the case report forms for "Additional Visit" should be filled out (in subject binder). These forms include:

AE form
Vitals form
Additional visit form
AE log

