5.4 Preparation and Administration of Study Drug

Study drug will be over encapsulated by the University of Iowa Pharmaceuticals (UIP) and stored and distributed by the University of Wisconsin Pharmaceutical Research Center and blinded according to a pre-designed scheme. Subjects will be randomized at the end of visit 1 (screening visit) and will receive study drug at their baseline physiology study visit (visit 3). UIP is an FDA-registered facility compliant with 21 CFR parts 11, 210, and 211, licensed by the DEA to handle controlled substances (Schedules I-V), and capable of handling potent/cytotoxic materials. UIP has been a cGMP facility for over 30 years.

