9.4 Data Collection at Sites

Data will be collected at Marshfield Clinic, Gundersen Health System, and Aurora Bay Care at the screening visit (Visit 1) and subject monitoring visit (Visit 4). In addition, 24-ambulatory blood pressure monitoring will be performed at each site (Visits 2 and 5). Data from these visits including subject demographic information, vital signs, laboratory test values, and other subject information will be uploaded into OnCore CRM clinical trial software. As a result all investigators will be able to access subject data from the screening visit and monitoring visit. It is vital that all investigators can access data from the monitoring visit for safety reasons and monitoring of the study medications. Data for the primary outcome variable will be uploaded into OnCore from Visit 3 and Visit 6 and will be made available for the data and safety monitoring committee when they meet quarterly and for interim/final analyses after 33%, 66%, and 100% of subjects have been enrolled.

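### The only numerical check on missing MSNA slopes, completers against LOCF, tries one fixed zero-change assumption, never varies it, and gives it too small a standard error

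*Combined protocol and SAP*

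**What the plan says.** Section 7.3 adopts an intention-to-treat philosophy and accepts that loss to follow-up may not be random. It offers two responses. One is descriptive: "We will try to determine if there is any cause for drop out and summarize the reasons accordingly". The other is the only numerical check: "comparing the analysis between dropping those with missing data and utilizing last observation carried forward". No analysis that varies the assumed outcome of drop-outs is mentioned.

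The primary variable (sections 3.2, 7.1 and 7.2) is the change in each subject's MSNA-SaO2 slope from baseline to week 6, compared by ANOVA. Section 9.4 gives its source: "Data for the primary outcome variable will be uploaded into OnCore from Visit 3 and Visit 6". The Visit 4 procedures in section 6.2 include no nerve recording. Under section 5.4, randomization takes place at the end of Visit 1, before any slope exists.

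Section 7.1 claims 90% power "if we had complete MSNA slope response data from 20 subjects per group", and plans 120 enrolled to reach 100 randomized. That allowance covers loss before randomization; no loss rate after randomization is stated.

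**The concern.** With only two measurement occasions, the last observation of anyone lost after Visit 3 is the baseline slope, so LOCF makes the change exactly zero. A randomized subject without a Visit 3 slope has nothing to carry forward, and section 7.3 does not say how such a subject is handled.

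The check therefore sets completers beside one fixed assumption. Under equal loss its expected estimate follows from the completers' means and the loss fraction alone, whatever the true reason for loss. The imputed zeros also enter the variance as if they had been measured. A reader who sees the two analyses agree would probably call the result robust, although the agreement is largely built in.

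Some loss after randomization is to be expected. Under section 3.1, subjects with defined creatinine or potassium rises at the two-week check "will have their participation in the study terminated. Subjects continuing in the study will then complete four additional weeks of drug therapy". Section 6.2 also allows procedures to be skipped, and section 3.2 requires an acceptable nerve recording.

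**Working it through.** **Inputs.** Section 7.1 gives a difference of 3.07 (1.13 v -1.94), alpha 0.017, 20 complete per group, 90% power, and an SD of 8-10 for the slope. The SD of the *change* is not stated.

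**Assumptions.** -1.94 is an active arm and 1.13 is placebo; tests are two-sided; 33 are randomized per arm (100/3); one active arm is compared with placebo by t test. Loss rates are illustrations.

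**The plan's own figure.** The 90% cannot be reproduced without an SD of change. Solving for it (noncentral t, n = 20 per group, alpha 0.017) gives about 2.55; 2.56 is used below. With an SD of 8-10 instead, power at 20 per group is about 12% to 8% (normal approximation).

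**Formulas**, with d the fraction lost in each arm:
- Completers: estimate -1.94 - 1.13 = -3.07; SE = SD × sqrt(2/(33(1-d))).
- LOCF: estimate -(1-d) × 3.07; variance per arm = [(1-d)SD² + d(1-d)mean²]/33.
- Delta analysis (each active drop-out is delta worse than active completers; placebo drop-outs behave like placebo completers): estimate -3.07 + d × delta. The completers' SE is kept, because a fixed delta adds no information.

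**Results at SD 2.56** (t in absolute value)

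| Loss per arm | Completers | LOCF | Delta = 3.07 |
|---|---|---|---|
| 20% | 3.07/0.705, t 4.36 | 2.456/0.585, t 4.20 | 2.456/0.705, t 3.48 |
| 13 of 33 | 3.07/0.810, t 3.79, p 0.0005 | 1.861/0.526, t 3.53, p 0.0008 | 1.861/0.810, t 2.30, p 0.027 |

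At SD 8 and 20% loss, completers give 3.07/2.202 = 1.39 and LOCF gives 2.456/1.768 = 1.39.

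LOCF and the delta 3.07 analysis have the same estimate. With 13 of 33 lost, the fall in t from 3.53 to 2.30 comes only from the standard error. The p of 0.027 lies above the 0.017 of section 7.1 and below the final threshold of 0.04507 in section 8.5.

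**Tipping delta at 0.017** = (3.07 - t-critical × SE)/d:
- 20% loss: (3.07 - 2.468 × 0.705)/0.2, about 6.7
- 30% loss: about 4.0
- 13 of 33 lost: (3.07 - 2.496 × 0.810)/0.394, about 2.7

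**How often the two planned analyses agree** (simulation, 200,000 trials per setting, alpha 0.017, SD 2.56 to 10). With equal loss of 7 or 13 per arm, they reach the same verdict in 99.2-99.9% of trials. With 10 active and 3 placebo lost, the figure is 95.0-98.6%. In that unequal setting, LOCF overturns about 1% of significant completer results at SD 2.56 and about 9-14% at SD 5-10.

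**The case against.** Several objections have force.

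- A reader might infer that the plan tries no departure from random loss. That is too strong: zero change for every drop-out is itself a non-random assumption. Under equal loss, the two planned estimates span active drop-outs who respond like active completers through to those who respond like placebo. What is missing is any variation beyond that, and a correct variance at the LOCF end.
- A reader might infer that the check can never warn. With unequal loss it sometimes does, as the 10 v 3 results show.
- LOCF is used only as a sensitivity comparison and is never named as the primary analysis, so the main result is not diluted.
- No passage forecasts loss of 13 in 33. Twenty complete per group is a power figure, and section 7.1 says the team will enroll as many as time allows.
- A reader might infer that the withdrawal rules will bias the comparison. The two-week laboratory check applies to all arms, and nothing in the documents ties those results to the MSNA slope. Symptomatic low blood pressure, listed under losartan in section 4.4.1, could just as well remove strong responders. The direction is unknown.
- Section 7.3 also says of incomplete hypoxia runs that "we will calculate the slope for that individual based on the data we were able to attain and use that in the final analysis". A reader might infer a bias from this. The text supplied gives no frequency of such runs and no response curve. The absence of weighting or matching is inferred from silence, with Appendix 1 not available. It does not carry the finding.

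These limit the size of the point. They do not make the completers-LOCF pair informative under equal loss, or correct its standard error.

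**Conclusion.** The point holds as a modest but worthwhile improvement. That LOCF means zero change for drop-outs with a Visit 3 slope, and supplies nothing for those without one, follows directly from the visit schedule. That its standard error is too small follows from counting imputed values as data. Neither depends on the assumed SD.

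The practical size does depend on it. At an SD of change near 2.56, the gap is small at 10-20% loss: at 20%, active drop-outs would have to do about 6.7 units worse than active completers, more than twice the whole assumed effect, to remove significance at 0.017. It becomes material if loss approaches the room between 33 randomized and 20 complete per arm, where the tipping delta is about 2.7 and p moves from 0.0008 to 0.027. At an SD of 8-10 the comparison is significant in 15% of simulated trials or fewer, so there is usually nothing to tip.

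**What to change.** Keep the ANOVA of change on available slopes as the main analysis. In section 7.3, replace LOCF with a delta-adjusted (tipping-point) analysis:

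- Multiply impute the week-6 slope from arm, baseline slope and CPAP stratum, with variance that reflects the imputation.
- Shift the imputed values by a range of deltas, separately by arm. Imputation without the shift would largely repeat the completers' result, so the shift is the essential part.
- Report the delta at which the conclusion changes, and judge its plausibility from the drop-out reasons that sections 7.3 and 9.3 already require.
- State how randomized subjects without a Visit 3 slope are handled.

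The cost is plan wording and a little more analysis work on data already being collected; trial conduct does not change.

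Optionally, for subjects with a partial hypoxia run, add a sensitivity analysis that computes both visits' slopes over the SaO2 levels completed at both. It costs precision and is not needed for this point.
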